4.1 Study Population

4.1.1 Intention to Treat (ITT) Cohort

The investigator will invite prospective patients to enroll in the study that meet the inclusion/exclusion criteria and have signed the informed consent. All patients randomized to either the investigational device (ArthroX Eclipse™ Shoulder Prosthesis) or the control device (ArthroX Univers™ II Shoulder Prosthesis) will be included in the ITT cohort. Randomization will take place after patients have been screened for inclusion and exclusion criteria. Patients found prior to randomization to not meet all inclusion and exclusion criteria will be defined as screen failures and will not receive the investigational device. These patients will be excluded from the ITT cohort.

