4.1.2 Per Protocol (Efficacy Evaluable) Cohort

Patients included in the ITT cohort but found to have been randomized in error will be excluded from the Per Protocol (Efficacy Evaluable) cohort. A patient will be considered to have been randomized in error if it is determined that the patient has clinically significant violations of the inclusion or exclusion criteria. Because approval and labeling is sought for patients meeting study inclusion and exclusion criteria, primary non-inferiority testing will be conducted in the Per Protocol (Efficacy Evaluable) cohort. Safety endpoints will be summarized for the Per Protocol cohort for the same reason. However, all adverse events that occur in the study will be reported in safety listings based on the ITT cohort.

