10.7 Safety Analysis

All safety endpoints will be summarized separately for investigational and control groups. Similarly, listings with details of the specific complications will be summarized separately as well.

The CCS Component Safety endpoint is any serious, definitely device-related adverse event within 24 Months of surgery. This will be evaluated at the exact two year anniversary (i.e., relative day 730) after the implantation surgery. The safety hypothesis of investigational verses control equality in the likelihood of serious device-related adverse event will be tested using a two-sided Fisher's Exact Test with Type I error rate set to $\alpha=0.05$.

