10.7.2 Adverse event detail listings

Adverse events listings will be provided for all patients in the ITT cohort and will provide details regarding adverse event type, relation to shoulder procedure, action taken, and clinical outcome. Separate listings will be constructed for adverse events with “definite” relationship to the device, “severe” adverse event, “severe device-related”, serious adverse events, and for all adverse events. The listing for all adverse events will be sorted by adverse event type.

Additional listings will be provided that include all adverse events among procedures requiring revision, removal, or replacement and all adverse events among patients who died.

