
1 A Month =30 days
 
2 Informed Consent (ICF) is obtained and signed prior to any study related procedures and a revised ICF is signed at the next study visit prior to any new or revised study related procedures.
 
3 Medication /Therapy Form will document at least 3 months of conservative treatment as required per Inclusion Criteria
 
4 SF 36, VAS and Constant may be done during unscheduled visit only if one of the required time points was missed, must document in deviation log
 
5 The only Pre-op laboratory require for the study is a pregnancy test if female and with child bearing potential. Pregnancy test may be done at V1 and or V2.
 
6 Data for Enrollment is collected at screening and confirmed at Visit 2 prior to Randomization
 
7 Randomization will occur on visit 2 after Inclusion/Exclusion criteria is confirmed
 
8 Operative detail is collected at Visit 2
 
9 Adverse Events are collected after subject has received treatment
 
10 All Radiographs must be done as per Radiographic Protocol inadequate Radiographs should be repeated within the time point window.
 
11 Radiographs must be available in medical record to validate Inclusion/Exclusion Criteria, if ordered during screening and results available to confirm eligibility prior to Randomization
 
12 The post-operative Radiographs must be done per Radiographic protocol and within 72 hours of surgery.
 
13 The Rehabilitation Plan is initiated on the evening of surgery –Refer to Appendix 2-2
 
14 If subject terminates prior to 24 months all end of study procedure and form are completed as if the subject completed 24 months.
								

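### Safety endpoints are summarised in the Per Protocol cohort, which removes implanted patients with clinically significant eligibility violations, and no implanted or as-treated safety set is defined

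*Combined protocol and SAP*

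**What the plan says.** Section 4.1.1 places all randomised patients in the ITT cohort and removes only those who fail eligibility beforehand: "Patients found prior to randomization to not meet all inclusion and exclusion criteria will be defined as screen failures".

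Section 4.1.2 then defines the Per Protocol cohort: "Patients included in the ITT cohort but found to have been randomized in error will be excluded from the Per Protocol (Efficacy Evaluable) cohort". The test for that label is whether "it is determined that the patient has clinically significant violations of the inclusion or exclusion criteria". Nothing exempts a patient who has already been implanted, and nothing says who decides, when, or with what knowledge of arm and outcome.

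The section justifies a Per Protocol primary test on the ground that labelling is sought for eligible patients. It carries the same reasoning over to safety: "Safety endpoints will be summarized for the Per Protocol cohort for the same reason". All adverse events are still to appear in ITT listings, and 10.7.2 repeats this: "Adverse events listings will be provided for all patients in the ITT cohort".

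Section 10.7 says "All safety endpoints will be summarized separately for investigational and control groups" and specifies a two-sided Fisher's exact test at 0.05 on serious device-related events. It names no cohort. Sections 10.6 (survival) and 10.7.1 (event counts) refer to relevant cohorts without naming them.

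**The concern.** Restricting an efficacy test to eligible patients can be argued from the intended labelling. The argument is weaker for safety, because harm in a patient who received the device is device harm whether or not that patient should have been enrolled.

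Several exclusion criteria concern bone quality or healing: humeral head cysts or lesions, osteoporosis, poor-healing disease, systemic steroids, infection. Section 5.1 itself ties loosening to bone stock and fracture to weakened bone. A patient implanted despite such a criterion may be at higher risk than the rest, and is the patient the safety summary would lose.

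The removal is also a judgement made after randomisation. An implant failure could prompt the chart review that finds the violation, and the documents contain no safeguard against that. At stake are the serious device-related event rate reported for each device and the test comparing them.

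**Working it through.** **Step 1. Which analysis covers an implanted violator?**

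| Output | Cohort in the documents | Implanted violator included? |
|---|---|---|
| Safety endpoint summaries (4.1.2) | Per Protocol | No |
| Serious device-related events, Fisher test (10.7) | Not named; 4.1.2 is the only stated rule for safety endpoints | No, if 4.1.2 governs |
| Event counts (10.7.1), device survival (10.6) | Relevant cohorts, unnamed | Undetermined |
| Adverse event listings (4.1.2, 10.7.2) | ITT | Yes, but no denominator, rate or test |

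No row is committed to the set of patients who received a device.

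**Step 2. The plan's own figures.** Section 10.4 assumes 88% success in both arms, margin 0.10, one-sided 0.05, 80% power and 2:1 allocation.

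- Control n = (1.645 + 0.842)² × 0.88 × 0.12 × (1 + 1/2) / 0.10² = 97.9, so 98. Eclipse = 196. Total 294, as stated.
- Inflation: 98/0.85 = 115.3, so 116; 196/0.85 = 230.6, so 231. Total 347, as stated.
- The allowance is 347 − 294 = 53 patients. It covers loss to follow-up and eligibility exclusions together, without a split. Section 10.4 expects few violations but gives no number.

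The documents therefore do not supply the number of implanted violators, nor any safety event rate.

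**Step 3. Size under stated assumptions.** Let v be the share of implanted patients who are violators, r the event rate in eligible implanted patients, and k·r the rate in violators. Assume everyone is implanted.

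- All-implanted rate = (1 − v)r + v·k·r. Per Protocol rate = r.
- Ratio of Per Protocol to all-implanted = 1 / (1 − v + v·k). It does not depend on r.

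| v (assumed) | k = 1 | k = 2 | k = 4 |
|---|---|---|---|
| 1% | 1.00 | 0.99 | 0.97 |
| 3% | 1.00 | 1/1.03 = 0.97 | 1/1.09 = 0.92 |
| 5% | 1.00 | 0.95 | 0.87 |
| 10% | 1.00 | 0.91 | 0.77 |

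If violators were at lower risk (k below 1), the ratio would exceed 1.

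**Step 4. Sensitivity of the Fisher test.** All event counts here are assumed and chosen to lie near the 0.05 threshold. Arm sizes are 231 and 116 from Step 2; section 3.1 allows control randomisation to stop earlier.

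- 9/231 Eclipse against 0/116 control: two-sided p = 0.032.
- Remove one implanted violator who had an event: 8/230 against 0/116, p = 0.056.
- Remove seven violators, two with events: 7/224 against 0/116, p = 0.10.

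This shows that one or two exclusions can change the test's conclusion. It does not show that they are likely to.

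**The case against.** The plan gives its labelling rationale openly, removes only clinically significant violations, expects few, and keeps every event visible in ITT listings. Many eligibility criteria, such as compensation claims or prisoner status, have no evident link to device safety. The unnamed cohorts in 10.6 and 10.7.1 may turn out to include ITT. All of this stands, and it limits the size of the problem. It does not supply a rate or test in everyone who received a device.

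A reader might go further in four ways that the documents do not support.

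- **That the cohort keeps never-implanted patients and dilutes the rate.** Sections 4.1.1 and 4.1.2 read literally allow this. However, 6.1.3 relabels a randomised patient given a non-study replacement as a screen failure, and 4.3 drops a patient converted to hemi-arthroplasty. Non-systemic events are counted per procedure (10.7.1), and randomisation takes place at the surgery visit, so the group should be small. What is shown is an unresolved conflict.
- **That a patient given the other device is counted under the assigned arm.** Section 10.7 does not say whether groups are as randomised or as treated.
- **That events after an abandoned implantation are not collected.** An Appendix 2-4 footnote says "Adverse Events are collected after subject has received treatment". But 9.1.1 defines adverse events over the course of the study whether or not device-related, 9.2 collects them on all subjects, and 9.3 requires a check at every encounter. The footnote needs reconciling; it does not prove non-collection.
- **That the understatement is large.** With 2 events in 7 violators and 4 in 224 others, the rates are 4/224 = 1.8% against 6/231 = 2.6%, about 31% lower. That needs 28.6% risk against 1.8%, a 16-fold ratio with no basis in the documents.

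**Conclusion.** The point holds in a limited form. Section 4.1.2 is an explicit rule that takes implanted patients with clinically significant eligibility violations out of the safety summaries, on an unblinded and otherwise unspecified judgement, and no exposed-patient safety set exists to offset it. Treating the 10.7 Fisher test as Per Protocol rests on 4.1.2 being the only cohort rule given for safety endpoints.

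The size is unknown. At an assumed 3% violators, the Per Protocol rate is 3% to 8% lower in relative terms at two to four times the risk, and equal if the risk is the same. The documents do not show which arm would benefit, so a bias in favour of Eclipse should not be inferred. The reason to act is that events may be sparse, one or two exclusions can matter, and the remedy is cheap.

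**What to change.** 1. In 4.1.2 and 10.7, define a Safety cohort: all patients in whom a study device was implanted or implantation was attempted, grouped by device received, or by device attempted if none was implanted.
2. Run the safety summaries, the serious device-related event rate and the Fisher test on this cohort. Keep Per Protocol as supportive. The main safety result then no longer depends on the eligibility judgement.
3. Name the cohorts meant in 10.6 and 10.7.1.
4. Reconcile 4.1.1, 4.1.2, 4.3 and 6.1.3 on how randomised patients not implanted as planned (non-study replacement, hemi-arthroplasty conversion) enter each analysis cohort.
5. Reconcile the Appendix 2-4 footnote on the start of adverse event collection with 9.1.1, 9.2 and 9.3.

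The cost is wording, one extra cohort flag and no new visits. Protocol amendments need FDA and IRB approval under 8.16, and a clarified collection rule cannot recover day-0 events that were not recorded for patients already operated on. The reported safety rate may become slightly less favourable.

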4.2 Study Subject Eligibility Criteria

Candidates must meet all eligibility criteria to be eligible for study participation:

4.2.1 Inclusion Criteria

1. The subject is ≥ 21 years of age
2. The subject has continued symptoms in target shoulder despite at least 3 months of other treatment modalities (e.g.: anti-inflammatory, physical therapy and steroid injections)
3. The subject has a diagnosis in the target shoulder of one or more of the following: osteoarthritis, avascular necrosis, post-traumatic arthritis, or rheumatoid arthritis. The above are defined as follows:

Osteoarthritis (Kellgren-Lawrence Grade 3 or higher), with clinical history of an absence of major trauma to the joint; symptoms of pain, stiffness, swelling and/or loss of motion; and with radiographic evidence of joint space narrowing, sub-chondral sclerosis, peripheral osteophytes with or without posterior subluxation of the humeral head.

Avascular Necrosis (Staging System of Cruess Stage IV or higher), with a clinical history of a known risk factor for avascular necrosis; symptoms of pain and loss of motion; and radiographic findings of flattening or collapse of the humeral head and joint space narrowing.

Post-Traumatic Arthritis (Kellgren-Lawrence Grade 3 or higher), with a clinical history of trauma to the targeted shoulder and subsequent pain, stiffness, swelling and loss of motion; and with radiographic evidence of joint space narrowing, sub-chondral sclerosis, peripheral osteophytes.

Rheumatoid Arthritis (American College of Rheumatology classification score of 6 or higher), with a clinical history that demonstrates: morning stiffness for at least 1 hour and present for at least 6 weeks, swelling, loss of motion, and/or serum rheumatoid factor; and radiographic findings of narrow joint space, peri-articular osteopenia, and/or peri-articular erosions and medial glenoid erosion.

4. The subject presents with pain and functional impairment in the index shoulder, measured by an Adjusted Constant Score of ≤ 50 . Note: The Adjusted Constant Score will be calculated from the raw Constant Score to establish patient eligibility.
5. The subject is willing to receive implantation of the ArthroX™ Shoulder Prosthesis or Uniers™ II Shoulder Prosthesis.
6. The subject must be physically and mentally willing and able to comply with all study procedures (including follow-up visits and radiographic assessments) until the conclusion of the study.
7. The subject has been informed of the nature of the study and provided written consent as approved by the sites local Institutional Review Board or Ethic Review Board.

4.2.2 Exclusion Criteria

1. The subject is likely a candidate for hemi-humeral arthroplasty (i.e.: Avascular Necrosis of the humeral head without glenoid involvement (Stages 0-3): Rotator Cuff Deficient Shoulder: Glenoid Bone deficiency/deformity that precludes glenoid replacement (Walch Type B2 or C) or Fractures of the Proximal Humerus, without Glenoid involvement.
2. The subject has immature bone as defined by the absence of cancellous bone patterning, a mature, thick cortex, and stress lines within the cancellous bone.

3. The subject has obvious defects in bone quality, such as cysts or lesions, in the humeral head of the target shoulder, as demonstrated by radiographic evaluation.
4. The subject has a target shoulder a rotator cuff that is not intact and not reconstructible.
5. The subject has Irreducible 3- and 4- part proximal humeral fractures of the target shoulder.
6. The subject has documented history of foreign-body sensitivity.
7. Subject with positive pregnancy test, or lactating, or intends to become pregnant during treatment period
8. The subject has documented diagnosis of Schizophrenia, Bipolar Disorder and/or Major Depressive Disorder as defined by DSM IV.
9. The subject is skeletally immature demonstrated radiographically by incomplete closure of proximal humeral epiphyses.
10. The subject is at high risk for poor healing or confounding outcomes (i.e.: clinically significant renal, hepatic, cardiac hematologic or endocrine disease).
11. The subject is on immune-stimulating or immunosuppressive agents
12. The subject has co-morbidity that reduces life expectancy < 36 month.
13. The subject seeking or receiving workman's compensation for shoulder injury,
14. The subject is \geq 350 lbs.
15. The subject engaged in heavy labor (e.g. repetitive lifting in the excess of more than 50 lbs.)
16. The subject has had surgery in the affected shoulder in the last 12 months (with the exception of a diagnostic arthroscopy without any reconstruction or repair procedures)
17. The subject is engaged in active sports participation. (e.g. weight lifting involving upper extremities or involved in contact sports)
18. The subject is taking medication known to potentially interfere with bone/soft tissue healing (e.g. steroids-with the exception of topical and /or inhalers)
19. The subject is a prisoners or wards of the state
20. The subject has a history document diagnosis of alcohol and/or substance abuse as defined by DSM IV
21. The subject has an active or chronic infection, either systemic or local.
22. The subject has Pathologic fractures of the affected shoulder
23. The subject has acute trauma of the affected shoulder
24. The subject has osteoporosis defined as a bone density T score of \leq -2.5. (A screening Questionnaire for osteoporosis, SCORE (Simple Calculated Osteoporosis Risk Estimation) and MORES (Male Osteoporosis Risk Estimation Score), will be used to screen patients who require a DEXA bone mineral density measurement.

Kellgren-Lawrence Scale

Osteoarthritis will be evaluated using the Kellgren-Lawrence Scale (Jacobson, 1996) as follows:

Grade of Osteoarthritis	Description
1	doubtful narrowing of joint space, possible osteophytic lipping
2	definite small osteophytes, possible narrowing of joint space
3	multiple moderately sized osteophytes definite joint narrowing, some sclerotic areas, possible deformation of bone ends
4	Large osteophytes, marked narrowing of joint space

Staging System of Cruess

Avascular Necrosis will be evaluated using the Staging System of Cruess (Cruess 1978)

Stage of Avascular Necrosis	Description
I	Documented only by magnetic resonance imaging or bone scan
II	Localized or mottled sclerosis, osteopenia
III	Crescent sign present, indicating a subchondral fracture
IV	Flattening and collapse of humeral head subchondral bone
V	Degenerative changes extending to glenoid side of joint

American College of Rheumatology

Rheumatoid Arthritis will be evaluated using the American College of Rheumatology (Aletaha 2010)

Joint Involvement (Choose option in each category)	Possible Points
1 large joint	0
2-10 large joints	1

1-3 small joints (with or without involvement of large joints)	2
4-10 small joints (with or without involvement of large joints)	3
> 10 joints (at least 1 small joint)	5

Serology (at least 1 test result is needed for classification)

Negative RF and negative ACPA	0
Low-positive RF or low-positive ACPA	2
High-positive RF or high-positive ACPA	3

Acute-phase reactants (at least 1 test result is needed for classification)

Normal CRP and normal ESR	0
Abnormal CRP or abnormal ESR	1

Duration of symptoms

< 6 weeks	0
≥ 6 weeks	1

4.3 Allowed Concomitant and Prohibited Treatments

The ArthroX Eclipse™ and Univers™ II Shoulder Prosthesis are to be performed as a total shoulder arthroplasty. A hemi-arthroplasty is prohibited except when the investigator determines operatively it is the best alternative for the subject. The alternative hemi-arthroplasty must be with a Univers™ II Shoulder Prosthesis only; the subject will be dropped as a study participant. The Investigational device, “Eclipse™ Shoulder Prosthesis” must never be implanted as a hemi-Arthroplasty.

Subject may not enter any other clinical trial involving medical or surgical intervention, or undergo any elective orthopedic surgery of target upper extremity while enrolled in this study. Observational studies will be considered with the sponsor’s approval.

Participation is restricted to having only one shoulder enrolled in this study.

4.4 Concomitant Analgesic

Use of medication for pain management (includes over the counter medications, prescription analgesics, narcotics, anti-inflammatories, muscle relaxants) will be recorded at each study visit. The data collected will include medication name, indication for use and dose.

This data is entered on the Concomitant /Medication form in the EDC. Medication used preoperative, operative and immediate postoperatively (while in recovery room) for target total shoulder replacement will not be collected during the study.

Additionally, concomitant treatment (physical therapy) will be recorded at each study visit. This data is entered on the Post-operative Evaluation Visit form in the EDC.

4.5 Subject Compensation

Each subject who returns for a follow up visit within the protocol required time frame will receive a reasonable compensation to offset the cost of meals, transportation, parking and other such expenses, as approved by the IRB. Compensation is provided to the subject by the investigational site. Compensation amounts are specified in the Informed Consent and the Clinical Trial Agreement.

4.6 DSM- IV -TR® Definitions :

4.6.1 Schizophrenia

Symptoms of Schizophrenia typically begin between adolescence and early adulthood for males and a few years later for females, and usually as a result of a stressful period (such as beginning college or starting a first full time job). Characteristic symptoms: Two (or more) of the following, each present for a significant portion of time during a 1-month period (or less if successfully treated):

- (1) Delusions
- (2) Hallucinations
- (3) Disorganized speech (e.g. frequent derailment or incoherence)
- (4) Grossly disorganized or catatonic behavior
- (5) Negative symptoms, i.e., affective flattening, alogia or avolition

Note: only one Criterion A symptom is required if delusions are bizarre or hallucinations consist of a voice keeping a running commentary on the person's behavior or thoughts, or two or more voices conversing with each other.

4.6.2 Bipolar Disorders:

Diagnostic criteria Bipolar I:

- A. Criteria, except duration are currently (or most recently) met for a Maniac, a Hypomanic, a Mixed, or a Major Depressive Episode.
- B. There has previously been at least one Manic Episode or Mixed Episode.
- C. The mood symptoms cause clinically significant distress or impairment in social, occupational, or other important areas of functioning.
- D. The mood symptoms in Criteria A and B are not better accounted for by Schizoaffective Disorder and are not superimposed on Schizophrenia, Schizophreniform disorder, delusional Disorder, or Psychotic Disorder Not Otherwise Specified.
- E. The mood symptoms in Criteria A and B are not due to the direct physiological effects of a substance (e.g., a drug of abuse , a medication or other treatment) or a general medical condition(e.g. hyperthyroidism)

For a diagnosis of Bipolar I disorder, a person must have at least one manic episode. Mania is sometimes referred to as the other extreme to depression. Mania is an intense high where the person feels euphoric, almost indestructible in areas such as personal finances, business dealings, or relationships. They may have an elevated self-esteem, be more talkative than usual, have flight of ideas, a reduced need for sleep, and be easily distracted. The high, although it may sound appealing, will often lead to severe difficulties in these areas, such as spending much more money than intended, making extremely rash business and personal decisions, involvement in dangerous sexual behavior, and/or the use of drugs or alcohol. Depression is often experienced as the high quickly fades and as the consequences of their activities becomes apparent, the depressive episode can be exacerbated.

Diagnostic criteria for Bipolar II:

Presence (or history) of one or more Major Depressive Episode

- A. Presence (or history) of at least one Hypomanic Episode
- B. There has never been a Manic Episode or a mixed Episode
- C. The mood symptoms in criteria A and B are not better accounted for by Schizoaffective Disorder and superimposed on Schizophrenia, Schizophreniform Disorder, Delusional Disorder, or Psychotic Disorder Not Otherwise Specified.

- D. The symptoms cause clinically significant distress or impairment in social, occupational, or other important areas functioning.

Bipolar II: Similar to Bipolar I Disorder, there are periods of highs as described above and often followed by periods of depression. Bipolar II Disorder however is different in that the highs are hypo manic, rather than manic. In other words, they have similar symptoms but they are not severe enough to cause marked impairment in social or occupational functioning and typically do not require hospitalization in order to assure the safety of the person.

